1.0 Objectives / Specific Aims

To address the major challenges in maintaining behavioral health and performance of crews on exploration-class missions, NASA has conducted extensive research in the areas of crew selection, training, and identifying behavioral issues in extreme environments^{1,2}. However, evidence from US and Russian spaceflight experience and data from space analog environments indicate that performance and behavioral issues are a significant risk for human space flight, no matter how well selected and trained crew members may be². While these symptoms may result in minor disruptions in Earth-based work environments, their significance becomes greatly magnified by the remoteness of space, potentially jeopardizing mission success and putting astronauts' lives in danger. Future exploration-class missions, such as a mission to Mars, are characterized by long mission durations (2 to 5 years); extreme isolation; hostile environment; extended periods of time within the confinement of the spacecraft; lack of contact with family; and limited social interactions beyond one's team members. There will be extreme performance pressures on crew members who must work optimally together as a team at all times. Therefore NASA must identify and validate countermeasures to promote behavior health and performance (NASA Human Research Roadmap: BMed1, BMed6). NASA has considered the inclusion of psychoactive medications for this purpose, however drugs may have expiration dates shorter than the mission length and the pharmacokinetics of drug administration in microgravity is poorly understood³ making non-pharmacological approaches desirable.

High frequency repetitive transcranial magnetic stimulation (rTMS) to left prefrontal cortex is a FDA-approved non-invasive brain stimulation for the treatment of major depression. A therapeutic course of rTMS typically consists of approximately 30-40 minutes of high-frequency (i.e., 10 Hz) treatment on each weekday, for 4 to 6 weeks. This protracted schedule often creates logistical hurdles for patients. Recently, a number of investigators have examined accelerated rTMS delivery. Sessions are repeated on the same day to reduce total days of treatment. Accelerated protocols have typically endeavored to fit the conventional dosing scheme (i.e., 54,000-60,000 pulses over 4-6 weeks) into a shorter time period ranging from 3 days to 2 weeks. In the case of either conventional or accelerated rTMS, there has been no systematic examination of dose response.

We propose that similar to novel drug development, advancing accelerated rTMS for enhancing neurocognitive function, stress resilience and to prevent the onset of neuropsychiatric symptoms (e.g., anxiety, depression, anger, irritability) fundamentally necessitates establishing the dose-response function for neurocognitive enhancement. Establishing this dose-response curve would enable the overall goal of study to develop and establish the efficacy of accelerated rTMS to left dlPFC as a non-pharmacological method for enhancing cognitive performance and resilience of high-performing, healthy adults of astronaut age and to extrapolate results to a spaceflight relevant environment (parabolic flight).

Aim 1. Establish the dose-response curve for an accelerated rTMS protocol to left dlPFC for enhancing neurocognitive performance and resilience in a group of adults that mimic the astronaut population. We hypothesize that neurocognitive performance and resilience to stress and psychopathology will show similar dose-response curves and that a dose that maximizes efficacy while minimizing burden will be demonstrated.

Aim 2. Examine the efficacy and safety of accelerated rTMS to left dlPFC for enhancing cognitive performance and resilience. We hypothesize that relative to sham TMS, accelerated rTMS to left dorsolateral prefrontal cortex (dlPFC) will show neurocognitive performance (primary outcome) and resilience enhancements (secondary outcome) in a group of healthy adults that mimic the astronaut population. We additionally hypothesize that accelerated rTMS will be safe as indexed by 1) no clinically significant structural brain changes; 2) no decrements in neurocognitive or affective function; 3) no significant adverse events. We hypothesize that frontal midline theta (and intersite phase synchrony) will be enhanced during successful feedback learning as shown on post- relative to pre- treatment EEG and more so under stress. Under threat, we also expect to see reduced stress as indexed by physiological measures of defensive reactivity (autonomic and startles reflex responding). We additionally hypothesize that active stimulation will be related to lower levels of self-reported stress and neuropsychiatric symptoms and greater resilience.

Aim 3. Assess the biological efficacy of TMS in a microgravity environment. During parabolic flight, resting motor threshold (rMT) will be measured for 10 subjects and compared to rMT obtained before and after flight on the ground. Any change in rMT during flight compared with pre- and post-flight values will be interpreted as an indicator of an altered physiological response to TMS during microgravity and will guide extension of the optimal ground-based accelerated rTMS protocol for spaceflight.

[figure not shown]

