To assess the biological efficacy of TMS during microgravity, we will determine resting motor threshold (rMT) in 10 subjects before, during and following parabolic flight (sessions 1-3). To determine rMT, we will briefly apply single pulse TMS. We will use a standard clinical algorithm (adaptive parameter estimation by sequential testing) to determine rMT of the abductor pollicis brevis muscle in an automated fashion. The measurement takes 20 seconds to perform (20 stimuli using single pulse TMS)^{75,76}.

Pre-flight data collection: First, on the ground pre-flight, the optimal location for stimulus induction will be identified. This location will be marked on the scalp in order to facilitate quick and reproducible identification of this site during the in-flight and post-flight sessions. At this location the TMS coil will be fixed firmly in place and the rMT will be determined. The subjects will also undergo a 10 minute standard computerized cognitive battery (WinSCAT) used by NASA to assess cognitive function in astronauts during International Space Station flights⁶⁰.

In-flight data collection: The in-flight rMT measurement will be performed by placing the coil in the same location identified pre-flight. The coil will be secured in place using stabilization hardware developed with Zero-G similar to the fixation hardware in use in our lab. The flight profile includes 30 parabolas each with approximately 25 seconds of microgravity. This will allow up to 2-3 in-flight measurements per subject providing a margin for human error.

Post-flight data collection: The same procedure will also be utilized to obtain the post-flight measurement. The subjects will also undergo a computerized cognitive battery (WinSCAT) post-flight.

Any significant change (based on established values in normal controls⁵⁴) in rMT during flight compared with pre- and post-flight values will be interpreted as an indicator of an altered physiological response to TMS during microgravity.

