[figure not shown]
Research activities during parabolic flight

Upon entering the aircraft, subjects and the research team will be directed to an area in the back of the plane which contains standard aircraft seating. Subjects and the research team will remain in this area during take-off and flight until the aircraft reaches an appropriate altitude. The subjects and research team will stay seated until signaled by Zero G personnel that it is time to move to the section of the plane where all experimental procedures will take place. At that time, the parabolic portion of the flight will begin.

For each parabola, Zero-G personnel provide the study team with adequate notice that the microgravity portion of the flight is approaching. This gives the research team time to get the subject in place in preparation for the upcoming TMS application. During TMS, the subject will be seated in a chair fixed to the floor of the aircraft and wear a seatbelt. (See the figure). The TMS coil will be securely fixed in place using an adjustable arm attached to the chair. The subject will place his/her head in a chin rest and forehead rest attached to the chair. The subject will hold their head against the TMS coil for the 20 seconds of TMS. One member of the research team will start the software which will control application of the TMS pulses and ensure the subject's head is in the appropriate position against the TMS coil. Another member of the research team ([name] or [name]) will closely monitor the subject for any discomfort or adverse event. After the 20 seconds of TMS, the subject will move from the experimental set up to the nearby designated location where subjects remain when not actively involved in the study as the research team prepares the next subject for the next parabola.

During parabolic flight, go-pro cameras will be used to video record the study.

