Arm 3. A power analysis was performed to determine the number of subjects needed to study physiological effects of simulated microgravity on motor threshold determination. With our study design, each subject will be his/her own control. For calculation of the study's power, we used data of Wassermann⁵⁴ who examined session-to session variability of motor threshold in 19 subjects on three separate occasions and computed the average coefficient of variation in motor threshold across sessions as 0.058 ± 0.036 . Based on this data, a total of 10 subjects will have a 99% chance (at a two sided 5% significance level) to detect a change in motor threshold due to an experimental intervention (parabolic flight) with an effect size of 1.61.

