MRI risks. Exposure to magnetic field strengths used in the present study is not shown to be a significant health risk. Risks to an unborn fetus from exposure to the MRI field strength used in the proposed research (3 Tesla) are unknown. Therefore, pregnant females and those who may become pregnant (unwilling to follow study restrictions limiting chances of conception) will not be allowed to participate. Participants will be asked to lie still and awake for 30 minutes in the scanner and this can occasionally result in soreness, stiff back, etc. Participants will be queried approximately every 10 minutes about their comfort. The main risk associated with MR imaging is the possibility of introducing metal to the magnet or its close proximity. Participants are thoroughly screened to prevent metal being brought into the MR environment. Other potential hazards of MRI scanning include: collision hazards, noise, neurostimulation at rapid sampling

rates (i.e., short TRs), body temperature changes, helium, and nitrogen hazards. The MRI facility is tested regularly by internal and external safety monitoring teams. These risks are minimal, and the facility is run within FDA guidelines. All investigators and research assistants running participants in the Center for Biomedical Imaging are thoroughly trained in MR safety as a requirement to run scans.

Risks associated with the parabolic flight (ZERO-G Experience®).

Injury or Illness. There is risk of injury or illness from sudden changes in gravity, altitude and/or turbulence, and could include physical contact of one's body with the interior of the aircraft and other participants during weightlessness, as well as objects and liquids floating in the aircraft. There is the danger of property damage, personal injury or illness (minor or serious) and/or death resulting from weightlessness, the conduct of the ZERO-G Experience®, flight malfunction or mechanical failure and/or anything else related to the ZERO-G Experience®. The risks of such Injuries & Damages are involved in such high adventure programs as the ZERO-G Experience® and subjects may have to exercise extra care for their own person and for others around them in the face of such hazards and that despite exercising such care Injuries & Damages may occur.

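### Arm 3 plans to read a flight-versus-ground change in motor threshold as a microgravity effect, but ground-only comparators cannot separate microgravity from other factors present only in flight

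*Combined protocol and SAP*

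**What the plan says.** Biological efficacy of TMS in microgravity is Arm 3's primary outcome (Section 3.0). Ten subjects have rMT measured on the ground, in parabolic flight, and on the ground again; in the words of the Section 10.0 power paragraph, "each subject will be his/her own control". Under Aim 3 in Section 1.0, a change in flight relative to the two ground values "will be interpreted as an indicator of an altered physiological response to TMS during microgravity", and it is to inform how the ground-based protocol is extended to spaceflight. The Arm 3 methods in Section 9.0 repeat the attribution but restrict it to a significant change, judged against published values from normal subjects. Aim 3 has no such qualifier.

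On the set-up, Section 9.0 says of the in-flight reading: "The coil will be secured in place using stabilization hardware developed with Zero-G similar to the fixation hardware in use in our lab". The passage on research activities during the flight adds: "The subject will hold their head against the TMS coil for the 20 seconds of TMS". The same passages describe a chair fixed to the floor, a seatbelt, a coil on an adjustable arm, chin and forehead rests, and a team member who checks head position. The scalp site is marked before the flight and reused.

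Section 2.0 says that the TMS field falls off quickly with distance from the coil (A1) and that its effect depends on the distance from coil to cortex (A5). Section 13.0 lists "sudden changes in gravity, altitude and/or turbulence" among the hazards of the flight, and motion discomfort as a separate risk.

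**The concern.** The rule fixes the cause before the data exist, and the design does not isolate that cause. Readings are taken either on the ground at normal gravity or in the aircraft during weightlessness. No in-aircraft reading at normal gravity, no hypergravity reading and no control flight is described. Microgravity and the other features of being in flight therefore always occur together.

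Coil seating matters most, because the plan's own background makes coil distance a determinant of the TMS effect. A small change in how the head meets the coil during a parabola could move rMT without any change in the subject's physiology.

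At stake is what the primary outcome of Arm 3 can support. Section 2.0 (A5) calls rMT the unit most commonly used for rTMS dosing and warns that estimating it wrongly can lead to over- or under-dosing. A shift read as a microgravity effect would be carried into the spaceflight protocol on that footing.

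**Working it through.** **Inputs**

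| Input | Value | Source |
|---|---|---|
| Subjects, power, alpha | 10; 99%; 5% two-sided | Section 10.0, Arm 3 |
| Effect size | 1.61 | Section 10.0, Arm 3 |
| Session-to-session variation | "coefficient of variation in motor threshold across sessions as 0.058 ± 0.036" | Section 10.0, Arm 3 |
| Comparators | ground, before and after flight | Section 1.0, Aim 3 |
| In-flight readings | up to 2–3, 20 stimuli each | Section 9.0, Arm 3 |
| In-flight exposure | at most 40 pulses | Section 13.0 |

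**Step 1: reproduce the stated power.** For a paired t-test, df = 10 − 1 = 9 and the noncentrality is 1.61 × √10 = 5.09. At two-sided 5% the noncentral t distribution gives 99.4%, which agrees with the stated 99%. The test is of a mean flight-minus-ground difference; nothing in it refers to the cause. The effect size also equals 0.058 / 0.036 = 1.61, the mean coefficient of variation over its ± value. The paragraph states no target change in rMT.

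**Step 2: what the contrast estimates.** The plan does not say how the two ground readings are combined; their mean is assumed here. Let μ be a subject's ground threshold, d a steady drift from the pre- to the post-flight reading, m the microgravity effect, and a the sum of all other effects present only in flight.

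- Pre-flight: μ + error
- Flight, about midway in time: μ + d/2 + m + a + error
- Post-flight: μ + d + error

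Flight minus the mean of pre and post = (μ + d/2 + m + a) − (μ + d/2) = **m + a** + error.

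The bracket removes steady drift. It does not touch a. More subjects or more repeats shrink the error term but leave m + a as one quantity, so the stated rule amounts to assuming a = 0.

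**Step 3: what belongs in a.** Coil seating has direct support from Section 2.0 (A1, A5). Altitude, turbulence and motion discomfort appear in Section 13.0 as risks to the subject, not as influences on rMT; that they could affect it is an inference. Fluid shift towards the head belongs in m, because Section 2.0 (A5) offers it as a route by which weightlessness may act.

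**Step 4: room for an in-flight reading at normal gravity.** The methods allow 2 × 20 = 40 to 3 × 20 = 60 stimuli, whereas Section 13.0 says at most 40. At 40 pulses there are 40 / 20 = 2 readings per subject. Using one in level flight would leave 2 − 1 = 1 in microgravity, with no spare.

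**The case against.** The strongest reply is that the plan already controls much of this. The methods require a significant change, which screens ordinary session variation. The scalp site is marked, the coil is held by an arm, the head is supported at chin and forehead, and staff check its position. Subjects with a history of motion sickness or a fear of flying are excluded (Section 4.0), and the ground readings bracket the flight.

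All of that stands, and it makes a smaller. It does not make a zero. A significance threshold does not identify a cause, a scalp mark fixes location but not contact or distance, and the bracket does not address effects confined to the flight. The readings in three body positions (Section 9.0) may help to interpret posture or fluid shift, but no setting, timing or analysis is given for them, and as described they are not an in-flight control.

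Three stronger readings are tempting and are not supported:

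- *Ground and flight readings use different hardware, with coil contact left to the subject.* The text likens the flight fixation to the laboratory's and does not say which rig serves the flight-day ground readings; the set-up figures are not available here. Contact is also supported and supervised.
- *A coil-contact shift is as large as the signal sought.* The 5.8% is session-to-session variation. No target change and no contact shift is given, so the comparison cannot be made.
- *Level flight must become the primary contrast.* Step 4 shows the cost. Section 9.0 describes no measurement window in level flight, since subjects move to the test area as the parabolas begin. Seating could also differ between level and weightless phases, so such a reading would not fully isolate m.

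**Conclusion.** The point holds as a limit on inference. The planned comparison can show that rMT differed under parabolic-flight conditions; it cannot by itself assign the difference to microgravity. This follows from the choice of comparators and does not depend on sample size or on the 99% power figure, which is arithmetically sound for a paired test.

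No magnitude is claimed. The conclusion rests on two readings of the documents: that in-flight TMS is delivered only in the weightless phase, as Section 9.0 describes, and that coil distance affects rMT, as Section 2.0 implies. A reader might infer that an in-flight change would be an artefact. The documents do not support that either: microgravity remains a plausible cause, but not the only one.

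**What to change.** 1. In Aim 3 (Section 1.0) and the Arm 3 methods (Section 9.0), replace the rule with: *a significant change will be interpreted as a change in rMT under parabolic-flight conditions; microgravity is one candidate explanation, alongside coil position and other flight factors.* Use the significant-change wording in both places.
2. Limit the Aim 3 statement about extending the protocol to spaceflight in the same way.
3. Where logistics allow, take the pre- and post-flight readings with the chair, head rest and coil arm used in flight, and say so. If this is already intended, one sentence settles it.
4. Optionally, add a normal-gravity reading in level flight as a supportive contrast. First reconcile the in-flight exposure statements in Section 9.0 (2–3 measurements of 20 stimuli) and Section 13.0 (at most 40 pulses).

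Items 1 and 2 cost only wording. Item 3 may need a schedule change: equipment loading ends at 5:00 pm the day before, and pre-flight collection runs from 8:30 am until security and boarding at 9:00 am. Item 4 would use an in-flight repeat now held as a margin for error and needs a measurement window that the plan does not describe.

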2.0 Background

A1. Transcranial magnetic stimulation. Transcranial magnetic stimulation (TMS) is a medical device that can safely and non-invasively stimulate the brains of awake individuals to induce neuroplasticity⁴ and is currently under investigation for numerous applications in behavioral health and performance⁵. Led by the pioneering efforts of our co-Investigator, [name], TMS first received approval from the U.S. FDA in 2008 for the treatment of depression^{6,7} and is now used in psychiatric departments throughout the US and Canada⁸. TMS is able to focally stimulate the cortex by creating a dynamic magnetic field generated by a brief but powerful electrical current passed through an electromagnetic coil⁹. The magnetic field induced by TMS diminishes rapidly as distance increases away from the coil. This allows TMS to be used in environments with complex equipment (like a space capsule) without interfering with other devices. For example, we have successfully used TMS to treat pain conditions inside the crowded intensive care unit^{10,11}.

TMS pulses induce a transient electric field in underlying excitable neuronal tissue. The affected area is approximately 2 to 3 cm below the device in superficial cortex¹², but neural effects are then triggered in interconnected brain areas. TMS pulses cause depolarization of cortical neurons at the stimulation site, which then propagate through connected network nodes¹³. Thus, TMS influences not only regional or local cortex, but also distributed neural networks. Repetitive TMS (rTMS) can further causally influence neural networks with the added power to produce neuroplastic periods of lasting excitation and/or inhibition that reliably persist after the termination of stimulation¹⁴.

The evidence-base for rTMS as a means of prompting therapeutic neuroplasticity has been most persuasive in the case of depression treatment. Proposed as a means of up- regulating prefrontal control over dysregulated limbic activation, high-frequency rTMS is most often applied to left

dorsolateral prefrontal cortex (dIPFC)¹⁵. Several meta- analyses have now shown that open-label effects sizes are large, while comparisons to sham stimulation are at least moderate to large among even patients highly resistant to pharmacotherapy^{16,17}.

[figure not shown]
craving¹⁹, posttraumatic stress disorder²⁰, borderline personality disorder²¹, and compulsive food restriction²².

The left dIPFC site typically targeted with rTMS is seated in an area of cortex integral to intact higher order cognition (i.e., executive function)²³. Co-I [name] has demonstrated that this left dIPFC region (as well as the rest of the cognitive control or multiple demand network) is commonly hypoactivated during cognitive tasks across neuropsychiatric disorders. This was observed in a transdiagnostic functional neuroimaging meta-analysis of more than 11,000 neuropsychiatric patients and matched control participants (Figure 1)²⁴. Furthermore, we have observed during functional magnetic resonance imaging (fMRI) concurrent with TMS, that TMS pulses to the left dIPFC cause BOLD activation in distributed regions of the cognitive control or multiple demand network (Figure 2; Badran et al., in preparation).

Even among healthy individuals for whom neurocognitive performance has a more restricted range, improved working memory performance has been observed after only a single session of excitatory rTMS^{25,26}. Regarding neurocircuit based effects, multiple sessions (i.e., 2 weeks) of excitatory rTMS to left dIPFC among a separate sample of healthy participants have been shown to enhance the efficiency of the cognitive control network during working memory performance²⁷.

A2. Repetitive TMS to target cognitive enhancement and resilience.

The proposed mechanism by which rTMS remediates depressive symptoms (i.e., up-regulating prefrontal control over dysregulated limbic activation) implies that rTMS should not only remediate depression, but should be a powerful transdiagnostic intervention for affective and cognitive dysregulation. In fact, high-frequency rTMS to left dIPFC is effective in reducing symptoms as far ranging as pain¹⁸, to

Taken together, it is not surprising that cognitive improvements have been reported as ancillary benefits to conventional²⁸⁻³⁰ as well as accelerated³¹ therapeutic rTMS for cognitively intact depressed patients. Accordingly, rTMS has also been shown to improve cognition as the primary outcome in studies of mild cognitive impairment³².

We propose that because rTMS to dIPFC is targeting cognitive neurocircuitry integral to adaptive cognitive functioning, that promoting neuroplasticity in this network with rTMS could be better optimized to both improve neurocognitive performance as well as enhance resilience to stress and neuropsychiatric dysfunction.

A3. Accelerated theta burst rTMS: Lessening intervention burden toward enhancing adherence amidst the demands of space flight. A therapeutic course of excitatory rTMS typically consists of a single treatment session on each weekday for four to six week. A single session lasts approximately 37.5 minutes with stimulation consisting of 10 Hz trains delivered for 4 seconds on and 26 seconds off. This schedule can be burdensome and reduce adherence. More recently, a number of groups have examined the safety, feasibility, acceptability, and effectiveness of accelerated rTMS delivery^{31,33-35} during which sessions are repeated on the same day to reduce total days of treatment, typically spaced by at least 30-60 minutes or more. Safety has also been assessed with both structural and metabolic imaging as well as neurocognitive testing, which has shown no adverse effects on neural integrity and, in fact, gains in cognition^{31,33-35}. Furthermore, acceptability results have suggested that accelerated protocols could increase adherence and decrease interruptions to daily obligations^{31,33-35}.

In a recent further innovation, intermittent theta burst (iTBS) rTMS has been shown to be as efficacious as 10 Hz rTMS in remediating depression³⁶. **Notably, a single session of excitatory iTBS rTMS entails 600 pulses in merely 3 minutes.** More specifically, pulses are delivered in triplets at 50 Hz for 2 s (i.e., 5 Hz triplets) and repeated every 10 seconds for a total of 190 seconds (600 pulses). Based on animal work, it has been proposed that theta burst stimulation may be particularly effective in inducing synaptic long-term potentiation due to potential mimicry of endogenous theta rhythms³⁷. Cortical theta rhythms as characterized in electroencephalography (EEG) are especially important in the support of human cognitive control^{38,39}. Furthermore, among healthy participants theta burst stimulation to left dIPFC has been shown to enhance working and recognition memory performance^{40,41}.

While the use of iTBS in accelerated protocols is only now emerging for the remediation of neuropsychiatric dysfunction, accumulating safety and efficacy results are promising, even among the most impaired and vulnerable patients⁴². From a practical standpoint, theta burst sessions are typically spaced by approximately 30 minutes to one hour or more with no requirements on the intervening time period. As such, astronauts could undergo multiple 3-minute sessions in a single day with limited interference on space flight demands.

To establish an efficacious intervention, tailored to the logistical demands of spaceflight, we propose two studies (Aims 1 & 2), each of which would implement a cutting-edge high-dose accelerated theta burst protocol for the application of rTMS to enhance neurocognitive performance and resilience to stress and neuropsychiatric dysfunction.

A4. A principled, empirical approach for determining rTMS dose. In the case of either conventional or accelerated rTMS, there has been no systematic examination of dose response. Rather, prior rTMS investigations have relied upon rational decision trees in determining TMS dose. For example, emerging accelerated protocols have typically endeavored to fit the conventional dosing scheme (i.e., 54,000- 60,000 pulses over 4-6 weeks) into a shorter time period ranging from 3 days³³ to 2 weeks³¹. While dose-response curves are typically interrogated as a function of efficacy relative to toxicity, it is also possible to model efficacy in the absence of toxicity, which would be most appropriate in the case of rTMS.

We propose that establishing the dose-response curve for enhancing neurocognitive performance among healthy, high functioning individuals, will most efficiently enable us to pinpoint the most efficacious and least burdensome dose to be administered.

A5. TMS and microgravity. Living in a microgravity environment has significant physiological effects on the human body⁴³⁻⁴⁵. For example, the pharmacokinetics of drug administration is altered in microgravity⁴⁶ and psychotropic medications are known to have reduced efficacy during spaceflight³. Likewise, there is the potential that TMS may operate differently in a microgravity environment. For example, studying the MRI brain scans of astronaut before and following spaceflight, we have recently shown there is a shift of brain tissue within the skull post-flight⁴⁷. This observed upwards shift of brain tissue could potentially alter the dosing of TMS as the effectiveness of TMS depends on the distance from the TMS coil (which is placed on the scalp) to the underlying cortex⁴⁸. In addition, cephalad fluid shifts which occur in astronauts⁴⁹ and during parabolic flight⁵⁰⁻⁵² may alter the neurophysiological response to TMS. Therefore, as part of this study we will investigate the physiological response to TMS in a microgravity analog environment (parabolic flight).

Several TMS measures of cortical excitability have been described; however the most basic is determination of the TMS resting motor threshold (rMT). The rMT is the minimal magnetic pulse causing muscle contraction as detected by electromyography (EMG) recordings. It is more formally defined as the amount of TMS machine output (intensity) necessary to produce a motor evoked potential (MEP) that exceeds a defined peak-to-peak amplitude (usually 50 μ V) 50% of the time in a finite number of trials. The rMT is believed to be an indicator of neuronal membrane excitability⁵³. Accurate estimation of rMT is of utmost importance in both research and clinical studies as it is the unit most commonly used for rTMS dosing⁵⁴. Inaccurate estimation of rMT can lead to subject/patient over- or under-dosing.

A6. Conceptual Model and Rationale for Design. We hypothesize that through up regulating cognitive control circuitry with rTMS that an astronaut would have enhanced capacity for successfully contending with the rigors of spaceflight. This would be evidenced foremost in enhanced cognitive control performance. The neurocircuitry undergirding efficient cognitive control overlaps with the neurocircuitry undergirding emotion regulation⁵⁵, and as reviewed, rTMS to dIPFC remediates a broad range of affective dysfunction. Thus, we further propose that

[figure not shown]

Figure 3. In order to optimize rTMS for neurcognitive enhancement, it is essential to determine the dose-response curve.

accelerated rTMS will promote stress resilience and prevent the onset of neuropsychiatric symptoms (e.g., anxiety, depression, anger, irritability).

Study Arm 1 would establish the dose-response for enhancing cognitive performance with accelerated rTMS to left dIPFC. Stress resilience will be utilized as a secondary outcome. Given the model it would also be reasonable to first establish the objective point at which resilience is up regulated by rTMS. We anticipate that healthy participants analogous to astronauts would likely show little variability in baseline resilience and affective dysfunction. We also anticipate that rTMS as proposed here could prevent the onset of stress and neuropsychiatric symptoms and thus we will longitudinally follow participants for the emergence.

Study Arm 2 would utilize the dose established in study one that maximizes cognitive performance gains while minimizing side effects and burden in a double blind, randomized controlled trial. Primary (neurocognitive performance) and secondary (resilience) outcomes would be identical to study 1. In addition, the impact of active versus sham iTBS on cognitive control and resilience under stress will be demonstrated during a challenging learning paradigm under threat of shock. EEG will be used to assess the impact on of iTBS on neurocircuit structure and function. Response stability will be assessed at 6 months and one year. To assess safety, structural MRI adverse event reporting, and cognitive measures will be collected over a long-term 6-month follow up period.

Study Arm 3 study would assess the biological efficacy of TMS in a microgravity environment during parabolic flight.

Study Arm 4 would establish the dose-response for enhancing cognitive performance with accelerated rTMS to left dIPFC, as well as assessing safety. In addition, the impact of each dose of iTBS on cognitive control and resilience under stress will be demonstrated during a challenging learning paradigm under threat of shock. MRI and EEG will be used to assess the impact on of iTBS on neurocircuit structure and function. Response stability will be assessed at 1 month post-treatment. Approval to combine studies 1 and 2 into a 4th arm was approved by our sponsor, due to recruitment delays caused by COVID-19.

B. INNOVATION AND ADVANTAGES AND RELEVANCE TO ASTRONAUTS

B1. Establishing a dose-response curve for rTMS. We propose to innovate in terms of establishing the dose-response curve for rTMS, instead of relying upon rational decision trees typically founded upon the rTMS for depression literature. At present there exists no empirical information as to the dose for maximal benefit in neurocognitive enhancement and stress resilience.

[figure not shown]

Figure 4. Conceptual Model

B2. Utilizing an accelerated rTMS delivery schedule. We propose to utilize an accelerated (high-dose) delivery schedule to lessen burden, increase adherence, and promote the utilization of this intervention during space flight with the counter measures NASA already has in place to promote behavior health and performance. Specifically, we propose to examine a range of rTMS doses all within a one-week delivery schedule.

B3. Utilizing an intermittent theta burst stimulation pattern. We propose to innovate by utilizing intermittent theta burst (iTBS), excitatory stimulation, which has been shown to be non-inferior to 10 Hz stimulation in the treatment of depression, but requires only three minutes/session.

